5.4 SAMPLES FOR GENETIC/GENOMIC ANALYSIS

5.4.1 Description of the scope of genetic/genomic analysis

Genomic sequence characterization is increasingly important in understanding tumor biology, host/microbial interactions, and skin conditions. The current study proposes to perform DNA sequencing on biologic samples, including stool samples – although the likelihood of incidental human genomic findings in stool sampling is expected to be very low/rare, the possibility for this is included in an abundance of caution.

The technology platforms used to interrogate genomic structure and function are dynamic and the specific methodology, e.g. DNA/RNA sequencing, DNA copy number analysis, DNA

methylation analysis, employed will be determined at the time that samples are ready for analysis.

5.4.1 Description of how privacy and confidentiality of medical information/biological specimens will be maximized

Confidentiality for genetic samples will be maintained as described (Section [5.3](#)). In addition, a Certificate of Confidentiality has been obtained for this study.

5.4.2 Management of Results

Subjects will be contacted if a clinically actionable gene variant is discovered. Clinically actionable findings for the purpose of this study are defined as disorders appearing in the American College of Medical Genetics and Genomics recommendations for the return of incidental findings that is current at the time of primary analysis. Subjects will be contacted at this time with a request to provide a sample to be sent to a CLIA certified laboratory. If the research findings are verified in the CLIA certified lab, the subject will be offered the opportunity to come to NIH (at our expense) to have genetic education and counseling to explain this result. If the subject does not want to come to NIH, a referral to a local genetic healthcare provider will be provided (at their expense).

This is the only time during the course of the study that incidental findings will be returned. No interrogations regarding clinically actionable findings will be made after the primary analysis.

6 DATA COLLECTION AND EVALUATION

6.1 DATA COLLECTION

- Eligible participants must be confirmed and checklist completed. Consent form must be signed prior to registration with Central Registration Information Services.
- Data will be secured in a 21 CR-Part 11-compliant data capture system provided by the NCI CCR. Data will be collected using protocol-specific case report forms, and verified for accuracy and completeness. Hard copies of data will be stored in locked secured areas and data will be entered onto a secured electronic data base. The following protocol-specific study forms will be complete and stored: eligibility checklist (developed by Central Registration Office, CRO). A copy of all serious AE forms will be kept in the research record.
- Treatment is given according to protocol (dated notes about doses given, complications, and clinical outcomes).
- Toxicity is assessed according to protocol (laboratory report slips, etc.)
- Response is assessed according to protocol (X-ray, scan, lab reports, and date noted on clinical assessment, as appropriate).
- Drug Accountability Records are kept for each participant.

The PI will be responsible for overseeing entry of data into a 21 CR-Part 11-compliant data capture system provided by the NCI CCR and ensuring data accuracy, consistency and timeliness. The principal investigator, associate investigators/research nurses and/or a contracted data manager will assist with the data management efforts. Primary and final analyzed data will have identifiers so that research data can be attributed to an individual human subject participant.

All adverse events, including clinically significant abnormal findings on laboratory evaluations, regardless of severity, will be followed until return to baseline or stabilization of event.

Document AEs from the first study intervention, Study Day 1, through 28 days after last dose of study treatment.

An abnormal laboratory value will be considered an AE if the laboratory abnormality is characterized by any of the following:

- Results in discontinuation from the study
- Is associated with clinical signs or symptoms
- Requires treatment or any other therapeutic intervention
- Is associated with death or another serious adverse event, including hospitalization.
- Is judged by the Investigator to be of significant clinical impact
- If any abnormal laboratory result is considered clinically significant, the investigator will provide details about the action taken with respect to the test drug and about the participant's outcome.

End of study procedures: Data will be stored according to HHS, FDA regulations, and NIH Intramural Records Retention Schedule as applicable.

Loss or destruction of data: Should we become aware that a major breach in our plan to protect subject confidentiality and trial data has occurred, this will be reported expeditiously per requirements in section [7.2.1](#).

6.2 DATA SHARING PLANS

6.2.1 Human Data Sharing Plan

What data will be shared?

I will share human data generated in this research for future research as follows:

- Coded, linked data in an NIH-funded or approved public repository.
- Coded, linked data in BTRIS (automatic for activities in the Clinical Center).
- Coded, linked or identified data with approved outside collaborators under appropriate agreements.

How and where will the data be shared?

Data will be shared through:

- An NIH-funded or approved public repository. Insert name or names: clinicaltrials.gov.
- BTRIS (automatic for activities in the Clinical Center).
- Approved outside collaborators under appropriate individual agreements.
- Publication and/or public presentations.

When will the data be shared?

- Before publication.
- At the time of publication or shortly thereafter.

6.2.2 Genomic Data Sharing Plan

Unlinked genomic data will be deposited in public genomic databases such as dbGaP in compliance with the NIH Genomic Data Sharing Policy.

6.3 RESPONSE CRITERIA

Response assessments will be performed per the schedules in the study calendars in **APPENDIX C**.

6.3.1 Disease Progression

- PSA will not be used to measure progression of disease. Participants will be offered androgen deprivation therapy (ADT) as clinically indicated. Starting ADT will be done at the discretion of the investigator, although this will result in treatment termination and removal from the clinical trial. Participants may go on ADT at any time, although this may result in removal from the trial. PSA will be used to calculate PSA kinetics/tumor growth kinetics.
- Development of a new bone lesion on bone scan.
- Development of a soft tissue mass, identified on CT scan or physical exam, consistent with metastatic prostate cancer. If identified on physical exam, the lesion may be biopsied to confirm the presence of prostate cancer.
- Development of urethral, ureteral, or spinal cord obstruction secondary to tumor.
- Development of cytologically positive pleural effusion or lymphangitic spread in the lungs.
- Symptoms which in the opinion of the investigator are consistent with clinical progression.

6.3.2 Intra-study PSA response

Participants will be monitored for PSA kinetics once enrolled. Participants who have an intra study decline in PSA will be evaluated for PSA response. Such responses would be defined by an intra-study apex PSA, which will be established by determining the maximum PSA value that can be validated by another intra-study PSA value within 10%. (The goal here is to not capture lab variations which may be seen as isolated PSA spikes (i.e. greater than 10%) in the context of participant follow-up. Responders will then be evaluated using confirmed PSA declines (at least 2 consecutive values after the intra-study apex) of at least 30%. Participants with intra-study PSA declines greater than 50% will also be identified.

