Prostvac is very well-tolerated, with common side effects of grade 1 injection-site reactions or flu-like symptoms.[11, 12] A favorable side effect profile and the potential ability to induce a sustained antitumor immune response, clinical trials are ongoing evaluating strategies to use Prostvac in earlier disease patients. A previous study of Prostvac in biochemically recurrent prostate cancer suggested that this treatment could slow/improve PSA doubling in 25 patients from a median of 5.3 months to 7.7 months.[13] A randomized prospective study is currently evaluating this hypothesis with the same treatment dosing and schedule as the previous study (NCT02649439). The treatment dosing and schedule for this combination immunotherapy study is the same as the previous studies.

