2.1.3 Additional Inclusion Criteria Specific to Biochemical Recurrence Cohort

2.1.3.1 Biochemical progression defined as follows:

- For participants following definitive radiation therapy: a rise in PSA of ≥ 2 ng/mL above the nadir (per RTOG-ASTRO consensus criteria)
- For participants following radical prostatectomy: rising PSA after surgical procedure (participants must have a PSA ≥ 0.8 ng/mL)

2.1.3.2 Participants must have a rising PSA as confirmed by 3 values a minimum of 1 week apart over at least a 1 month period of time.

2.1.3.3 Participants must have a PSA doubling time of 5-15 months.

2.1.3.4 ECOG performance status of 0–1 (Karnofsky $\geq 80\%$, see [APPENDIX A](#)).

2.1.3.5 Negative CT scan/MRI and bone scan for metastatic prostate cancer.

2.1.3.6 Baseline testosterone ≥ 100 ng/dL.

2.1.3.7 PSA ≤ 30 ng/mL.

2.1.3.8 Hematological eligibility parameters (within 16 days before starting therapy; see [APPENDIX D](#)):

- Granulocyte count $\geq 1000/\text{mm}^3$
- Platelet count $\geq 100\,000/\text{mm}^3$
- Hgb ≥ 10 g/dL

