begin C1D1 with vaccine therapy. In this case, the 3 PSA values obtained prior to enrollment will be evaluated as if they were collected during the surveillance period while enrolled and will factor into the determination of the intra-study apex value (See Section 6.3.2) highest PSA that is within 10% of another peak PSA for the participant on-study. Any other peak PSA values that are beyond 10% of other PSA values on the study will be determined as potential lab variability and excluded from response assessment.

- With Amendment v05/10/2023, participants that have at least 3 PSA measurements in the surveillance period, with at least one of them sufficient to provide the doubling time from baseline, will not undergo any further PSA measurements in the surveillance period.

Prostvac will be administered nearly identical to the Phase III dosing with Prostvac-V given day 1 (week 1) followed by Prostvac-F on weeks 3 and 5 then monthly for an additional 5 months. Therefore, Prostvac-V is given one time (priming vaccine) followed by 7 doses of Prostvac-F (booster vaccine). The administration schema for CV301 is representative of the Phase I dose escalation trial. MVA-BN-CV301 (priming vaccine) is administered on day 1 (week 1) and week 3 followed by FPV-CV301 (booster vaccine) administered on week 5 then monthly for an additional 5 months.

MSB0011359C (anti-PDL1 TGF β Trap) will be administered at the recommended phase II dose of 1200mg by IV infusion every 2 weeks for 3 months (6 doses) starting after 4 months of concurrent Prostvac and CV301.

Effective with amendment v7/29/2021, MSB0011359C will no longer be given as part of the treatment combination for the Biochemical Recurrence cohort (Arms 2 and 3). This cohort will now receive Prostvac and CV301 during months 1-7 following surveillance.

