18 APPENDIX C: ON STUDY AND FOLLOW-UP EVALUATIONS

18.1 STUDY CALENDAR: BIOCHEMICAL RECURRENCE COHORT

	Screening	Baseline	Surveillance for 4 months ²⁰				Vaccines for 7 months							End of treatment ¹	Follo w-up ¹⁴	
			M -4	M -3	M-2	M-1	C1 D1	C 1 D 15	C2 D1	C3 D1	C4 D1	C5 D1	C6 D1	C7 D1		
Informed Consent / Registration	X															
NIH Advance Directives Form ¹³	X															
TREATMENT																
Prostvac-V ²							X									
Prostvac-F ³								X	X	X	X	X	X	X		
MVA-BN-CV301 ⁴							X	X								
FPV-CV301 ⁵									X	X	X	X	X	X		
EVALUATION																
History and PE, Weight	X ⁸	X ⁹		X		X	X	X	X	X	X	X	X	X	X	X
ECOG Performance Score	X ⁷	X ⁹														
Pathologic confirmation of dx	X ⁶															
Laboratory Testing																
CBC with differential	X ⁸	X ⁹					X	X	X	X	X	X	X	X	X	X
Acute Care Panel	X ⁸															
Hepatic Panel	X ⁸															

Abbreviated Title: Combination Immunotherapy

Version Date: 05/10/2023

	Screening	Baseline	Surveillance for 4 months ²⁰				Vaccines for 7 months								End of treatment ¹	Follow-up ¹⁴
			M -4	M -3	M-2	M-1	C1 D1	C 1 D 15	C2 D1	C3 D1	C4 D1	C5 D1	C6 D1	C7 D1		
Serum chemistries (Na ⁺ , K ⁺ , Cl ⁻ , CO ₂ , glucose, BUN, creatinine, albumin, calcium, magnesium, phosphorus, alkaline phosphatase, ALT, AST, total bilirubin, LDH, CK, uric acid, total protein)		X ⁹					X	X	X	X	X	X	X	X	X	X
Serum amylase and lipase		X ⁹					X	X	X	X	X	X	X	X	X	X
Serum thyroid stimulating hormone (TSH)		X ⁹					X	X	X	X	X	X	X	X	X	X
Urinalysis		X ⁹														X
Serum PSA and Testosterone	X ⁸	X ⁹	X	X	X	X	X	X	X	X	X	X	X	X	X	X
Hep B/Hep C, HIV	X ⁷															
Lymphocyte Phenotyping (CD4/CD8)		X ⁹					X	X	X	X	X	X	X	X	X	X
PAP (prostatic acid phosphatase)		X ⁹					X	X	X	X	X	X	X	X	X	X
ECG		X ¹⁰														
Tc 99 scintigraphy	X ⁷						X ²¹								X	X ¹¹
CT-C/A/P	X ⁷						X ²¹								X	X ¹¹
¹⁸ F-DCFPyL PET scan			X ¹⁹												X ¹⁹	

	Screening	Baseline	Surveillance for 4 months ²⁰				Vaccines for 7 months							End of treatment ¹	Follow-up ¹⁴	
			M -4	M -3	M-2	M-1	C1 D1	C1 D1	C2 D1	C3 D1	C4 D1	C5 D1	C6 D1	C7 D1		
NaF PET scan			X ¹⁵													X ¹⁵
Research Bloods		X ¹⁶					X ¹⁶		X						X ¹²	X ¹²
Research stool sample collection (optional) ¹⁸			X						X						X	
Adverse Events	X			X		X	X-								→	X
Concomitant Medications	X						X-								→	X
FACT-P survey		X ¹⁷					X ¹⁷			X ¹⁷			X ¹⁷			
MSK Anxiety Survey		X ¹⁷					X ¹⁷			X ¹⁷			X ¹⁷			

1 cycle = 28 days; C=Cycle; D=Day; M = month (28 days)

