Participant visits may be delayed for up to 2 weeks for logistical reasons during the surveillance period. While participant is receiving immunotherapy, visits and treatment may be -/+3 days in the first cycle around the scheduled visit. Participants being evaluated after cycle 1 may have their follow-up visits adjusted by +/-7 days for logistical purposes. Laboratory tests specified for each cycle may be performed up to 5 days prior to the start of each cycle for logistical purposes. For participants who do not receive treatment during this window, the dose will be considered missed and the next visit will occur at the next scheduled time.

Footnotes:

- ¹ End of treatment visit will occur 28 days (-/+14 days) following the last dose of immunotherapy. Willing participants will continue to be followed after cycle 7 until progression or ADT is clinically indicated.
- ² Prostvac-V 2 x 10⁸ infectious units/ 0.5 mL by subcutaneous injection.
- ³ Prostvac-F 1 x 10⁹ infectious units/0.5 mL by subcutaneous injection.
- ⁴ MVA-BN-CV301: one dose is four sites of subcutaneous injection each consisting of 4 x 10⁸ infectious units/0.5 mL.
- ⁵ FPV-CV301 1 x 10⁹ infectious units/0.5 mL by subcutaneous injection.
- ⁶ Pathologic confirmation will be obtained any time prior to enrollment.
- ⁷ Screening assessments obtained within 8 weeks prior to enrollment.
- ⁸ Screening assessments obtained within 16 days prior to start of enrollment.

⁹ Baseline assessments obtained within 16 days prior to treatment (these tests will not need to be repeated if they were done at screening within the appropriate timeframe).

¹⁰ Baseline ECG will be obtained within 8 weeks prior to enrollment

¹¹ Follow-up Imaging will be done prior to vaccine therapy (cycle 1), and at the end of study visit. During the follow-up period, imaging will be done every 6 months for 1 year then as clinically indicated. A window of +/- 21 days for imaging is allowed. Restaging scans may be completed earlier if clinically indicated.

¹² Optional

¹³ As indicated in section **12.3**, all subjects will be offered the opportunity to complete an NIH advance directives form. This should be done preferably at baseline but can be done at any time during the study as long as the capacity to do so is retained. The completion of the form is strongly recommended but is not required.

¹⁴ See Section **3.4** for further details on follow up visits.

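### The 10% apex check in 6.3.2 and 3.1 can drop a true late PSA peak in men doubling in 5 to about 6–7 months, so some real declines of about 30–40% would be scored as non-response if that rule governs

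*Combined protocol and SAP*

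**What the plan says.** Section 6.3.2 defines the apex as the highest PSA "which will be established by determining the maximum PSA value that can be validated by another intra-study PSA value within 10" per cent. Its stated purpose is to avoid capturing isolated laboratory spikes. Response then requires "confirmed PSA declines (at least 2 consecutive values after the intra-study apex) of at least 30" per cent. Section 3.1 repeats the matching test and says that peaks failing it "will be determined as potential lab variability and excluded from response assessment". Neither section says whether the 10% is taken of the peak or of the matching value.

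Section 2.1.3.3 sets the eligible range: "Participants must have a PSA doubling time of 5-15 months". The calendar in 18.1 schedules PSA at M-4 to M-1, C1D1, C1D15, C2D1 to C7D1, end of treatment and follow-up, with 28-day cycles and months. Section 3.7 makes follow-up monthly for five months.

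Section 10 defines the counted event differently. Sections 10.2, 10.4.1 and 10.4.2 all take a fall of at least 30% from the maximum to the minimum PSA, with no matching check and no confirming values. Section 10.1.1, however, states the primary objective as a confirmed decline. No section says which definition scores the primary endpoint.

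**The concern.** The matching test assumes that a genuine peak has a neighbour within 10% and that only an assay spike stands alone. For the fastest-growing eligible men, PSA rises by more than 10% between visits without any spike. Their last value before a decline can therefore look like an outlier, be set aside, and leave the decline measured from a lower value that may already be on the way down.

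The error is selective by doubling time and always lowers the apex, so it can only under-count responders. With a cut-off of 7 responders in 25, a few lost responders could change the conclusion if this rule scores the primary endpoint.

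**Working it through.** **The plan's own figure.** Inputs from 10.2: n = 25, 15% against 35%, one-sided 0.10, exact binomial. Six or more responders has probability 0.162 at 15%, which is too high; seven or more has 0.070. Power = P(Bin(25, 0.35) ≥ 7) = 82.7% (stated 82%). The one-sided 90% bounds for 7/25 are 16.3% and 42.6%, as stated.

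**Growth between visits.** Growth = 2^(gap/DT) − 1, with gap = 28/30.44 = 0.92 calendar months:

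- DT 5 months: 13.6%
- DT 6 months: 11.2%
- DT 6.5 months: 10.3%
- DT 7 months: 9.5%

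**Threshold doubling time.** If the 10% is of the lower value, 0.92 × ln 2 / ln 1.10 = 6.7 months. If it is of the peak, 0.92 × ln 2 / ln(1/0.9) = 6.05 months. Counting doubling time in 28-day months gives 7.3 and 6.6. Hence about 6–7 months.

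**Where the calendar protects a peak.** Over the 14-day gaps C1D1–C1D15 and C1D15–C2D1, growth at DT 5 is 2^((14/30.44)/5) − 1 = 6.6%, so a C2D1 peak always has a match. A C1D1 peak is protected if a separate baseline PSA is drawn within 16 days before treatment (7.6% growth over 16 days at DT 5). From C3D1 onward the preceding value is a full 28 days earlier.

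**One track.** DT 5 months, peak at C5D1 set to 1.00, then a fall of 30% per visit to a floor 40% below the peak (assumed shape, no assay noise):

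- C1D1 0.600, C1D15 0.640, C2D1 0.682, C3D1 0.775, C4D1 0.880, C5D1 1.000, then 0.70, 0.60, 0.60, 0.60.
- The peak's neighbours are 0.880 (1.000/0.880 = 1.136) and 0.70. Neither is within 10% on either base.
- 10% of the lower value: 0.880 and 0.775 also fail (0.775/0.70 = 1.107). The apex is 0.70, matched by 0.682. Scored fall: 1 − 0.60/0.70 = 14%.
- 10% of the peak: 0.775 is matched by 0.70 (9.7% below). Scored fall: 1 − 0.60/0.775 = 23%.
- On both bases a sustained 40% fall is a non-response. Under Section 10's raw definition it is a success.

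**A grid of tracks.** Noise-free, DT 5 months, falls of 5–40% per visit to floors 32–60% below the peak. Real, confirmed declines of at least 30% that the rule misses, with the 10% taken of the lower value (of the peak in brackets):

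- Peak at C2D1: 0/30
- Peak at C3D1: 10/30 (8/30)
- Peak at C5D1: 15/30 (11/30)
- Peak at C7D1: 15/25 (11/25)
- DT 7 months or longer, any of these peaks: 0

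These counts describe assumed shapes; they are not miss rates.

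**With assay noise.** A simulation assuming 5% CV, DT 5–6 months and a 35% fall from a peak at C3–C6 scored 32–42% of men as responders under the rule. It scored 59–84% when a peak could also be accepted against the man's own projected growth, with no rise in false responses. Falls of 50% or more were still scored in 95–99%.

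**Power if 6.3.2 scores the primary endpoint.** Let f be the share of responders in the fast band and m the share of those missed. Power = P(Bin(25, 0.35(1 − f·m)) ≥ 7). The documents give neither f nor m. Uniform doubling times over 5–15 months would give f = (6.7 − 5)/10 = 17%.

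| f (assumed) | m = 25% | m = 50% | m = 100% |
|---|---|---|---|
| 10% | 80.2% | 77.6% | 71.7% |
| 17% | 78.4% | 73.5% | 62.0% |
| 35% | 73.2% | 61.3% | 33.6% |

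**The case against.** The strongest reply is that the primary analysis never uses this rule. Sections 10.2, 10.4.1 and 10.4.2 count a fall from the raw maximum to the raw minimum, under which the man in the track above is a success and power stays at 82.7%. That stands as a reading of Section 10. It does not close the matter, because 10.1.1 requires confirmation, only 6.3.2 defines it, and 3.1 excludes unmatched peaks from response assessment in general terms.

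A reader might infer that every real 30% decline in a fast-doubling man is lost. The documents do not support that. Any intra-study value can validate the peak, including the first falling one: a fall of 5% per visit loses nothing. An unmatched peak lowers the apex but does not make the man unscorable, so deep falls still count. Early peaks are largely protected, and slower growth on treatment would bring neighbouring values within 10%.

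A reader might also infer that such men are common, because Section 1.2.3 reports that Prostvac "could slow/improve PSA doubling in 25 patients from a median of 5.3 months to 7.7 months". That is another study whose entry criteria are not given, and men doubling in under 5 months are ineligible here. The doubling-time mix in this trial is unknown.

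Finally, the rule is a stated and conservative choice. Its error runs toward under-counting, so it does not inflate the one-sided type I error. That is fair, and it limits the severity.

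**Conclusion.** The concern holds in a limited form. Under 6.3.2 and 3.1, a man doubling in 5 to about 6–7 months whose true peak is at C3D1 or later has no preceding value within 10% of it. If the first falling value also fails to match, some real declines of about 30–40% become non-responses. This assumes that growth continues at the pre-treatment rate up to the peak.

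The effect on the primary test is conditional. It is nil if Section 10's wording governs. If 6.3.2 governs, power is about 78% to 74% on the assumption that 17% of responders are fast doublers and 25–50% of them are missed. A larger power loss might be inferred from the lower rows and last column of the table, but those inputs are assumptions with no source in the documents. The unresolved conflict between 6.3.2 and Section 10 is what leaves the size open. This should be fixed, but it is not a must-fix.

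**What to change.** 1. Name one response definition for the primary endpoint and use it in 6.3.2, 3.1, 10.2, 10.4.1 and 10.4.2. State whether the 10% is of the peak or of the matching value.
2. Wherever the apex check is kept, retain a peak that is within 10% of another intra-study value, or within 10% of the value projected to that date log-linearly from the participant's own preceding PSA values. Exclude it as laboratory variability only if it fails both. State the fitting window and the minimum number of values for the projection. In the track above, the preceding values project to 1.00, so the peak is kept and the 40% fall counts.
3. Keep the confirmation by two consecutive values, which already guards against isolated low readings.

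The cost is a few sentences and a small programming change, with no new data. The downside is that a few borderline peaks now dropped would be retained, and the projection rests on an estimated growth rate. The change should be made before responses are scored.
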